9.8 Safety Assessments

Laboratory Test Results

Blood and urine will be collected at Screening, Baseline (blood only), Treatment Day 1 -T0 (urine only), Treatment Days 1, 2, 3, 4 and 5, at the Completion of the Last Infusion, and 24 hours Following the Completion of the Last Infusion (or Treatment Discontinuation date) for safety laboratory tests to be conducted at local laboratories. Safety assays include:

- Liver function tests (LFTs): Total bilirubin, alkaline phosphatase, alanine aminotransferase (ALT/SGPT), aspartate aminotransferase (AST/SGOT);
- Coagulation: Prothrombin time reported as the international normalized ratio (INR); and
- Urinalysis: dipstick plus microscopic evaluation of sediment if clinically indicated.

Any laboratory test result considered by the investigator to be clinically significant should be considered an AE.

If clinically significant abnormal laboratory values occur during the trial, the patient may be retested regularly until repeat test results return to normal, stabilize, or are no longer clinically significant.

Other Safety Assessments

Vital signs (blood pressure, temperature, heart rate, and respiration) will be measured at Screening, Baseline, Treatment Days 1, 2, 3, 4 and 5, at the Completion of the Last Infusion, and 24 hours Following the Completion of the Last Infusion inclusively. Height will be measured once (at Screening).

Physical examinations will be performed at Screening, Baseline, Treatment Days 1, 2, 3, 4 and 5, at the Completion of the Last Infusion, and 24 hours Following the Completion of the Last Infusion, inclusively (or Treatment Discontinuation Visit).

Single 12-lead ECGs will be performed at Screening, Baseline, Treatment Days 1, 2, 3, 4 and 5, at the Completion of the Last Infusion, and 24 hours Following the Completion of the Last Infusion, inclusively and will be evaluated locally according to usual site procedures.

Inter-current Illness and Pre-Existing Diseases

Inter-current illnesses, including signs/symptoms of a pre-existing disease state (medical history), that are present at or before study drug administration (including those that manifest between signature of the informed consent and administration of study drug) are to be recorded as medical history/pre-existing conditions. Those events that manifest with the same severity, frequency, or duration subsequent to study drug administration need not be recorded as AEs. However, incidents for which there is an increase in severity or duration of the inter-current illness or pre-existing disease must be reported on the AE CRF.

10 DATA MANAGEMENT

10.1 Data Processing

Data management is handled by the Data Coordination Unit (referred to in this document as the SDCC), which is housed in the Department of Public Health Sciences at the Medical University of South Carolina (MUSC). All activities are conducted in coordination with the Trial Executive Committee and the Clinical Centers. Case Report Forms (CRFs) have been developed by the SDCC with input from the Trial Executive Committee. Electronic copies of the CRFs are made available to the Clinical Centers via the WebDCU™ to be used as worksheets for capturing data for the Trial. The study database has been developed in Microsoft SQL Server based on the approved CRFs. This system allows for web-based data entry and management. The data are captured and entered (single keyed) at the Clinical Centers via the web interface. Data must be entered into the database at the Clinical Centers within 5 days of assessment/data collection. The data are managed (including data queries) by the SDCC staff using a secured Trial website.

During the design of the database, automated consistency checks and data validation rules are programmed to check for potential data errors, including missing required data, data out of pre-specified range, data conflicts and disparities within and among the CRFs. All validation rules are outlined in the Data Management Plan generated by the SDCC. In addition to the study database, the SDCC provides the Clinical Center staff access (via password) to a standard set of web-enabled tools, including patient visit calendar, accrual status, CRF completion status, and outstanding DCR status pertaining to their respective Centers.

The SDCC develops, validates, and maintains the study database and provides independent oversight and management of the flow, entry, and quality assurance of data collection activities. The SDCC also provides statistical support, including reports to the SRC and Medical Safety Monitor; and, where necessary, shields blinded investigators from access to unblinded data during the performance of the trial. The SDCC is responsible for the enrollment scheme, final statistical analysis plan and final data analysis.

10.2 Data Security and Confidentiality

During the course of the trial, user access to the files with patient identifiers, treatment assignment and files with study outcomes will be restricted to core staff with any exceptions to be approved by the Executive Committee.

In addition to use of passwords and other security measures, all documents containing identifying information on individuals or physicians are considered confidential materials and will be safeguarded to the greatest possible extent. No information, which identifies a specific person, hospital, or physician, will be released to, or discussed with anyone other than study staff members.

Because the SDCC uses a web-based system, source documents and CRFs will remain at the participating sites. The study database only identifies study patients by unique study identification codes. All data will be stored in a manner that is HIPAA compliant, without the ability to track the information back to a specific patient except through a password protected system. All collected information about a patient will be stored by a unique identification code.

All SDCC personnel are certified by the NIH Office of Human Subjects Research in the Protection of Human Research Subjects course.

10.3 Data Quality Assurance

Upon entry of CRFs into the study database, quality control procedures will be applied at each stage of data handling in order to ensure integrity of the study data and document processing system reliability. An appointed site monitor will perform reviews of source documents and case report form information at the sites to confirm accuracy of data capture. The STOP-ALF Site Monitoring Plan details the monitoring plan and facilitates compliance with Good Clinical Practice (GCP) guidelines, applicable FDA regulations (21 CFR 812 and 813), and the FDA's "Guidance for Industry: Oversight of Clinical Investigations - A Risk-Based Approach to Monitoring". The monitoring plan includes a combination of central, remote and on-site monitoring, and these findings will be used to identify and correct problems in data collection.

To ensure monitoring responsibilities are performed to the fullest extent possible, an experienced independent clinical research associate(s) (monitor) performs data verification for the trial either on-site or remotely, should direct access to patients' electronic medical records be permitted by the institution. For the first evaluable patient enrolled at any site, 100% of the data will be verified to source documents. For subsequent patients, a checklist of key outcome and safety data variables requiring source document verification (SDV) has been developed based on the trial's safety and efficacy endpoints. The checklist ensures that a target of no less than 40% of the clinical data submitted to the STOP-ALF database are verified against source documents at the performance sites prior to finalization of the database. Of the data on the checklist, the safety and efficacy variables represent approximately half of the data to be verified. The remaining half of source monitored data include: 100% of deaths and 100% of serious adverse events and source data reviews based on the per-patient evaluation of safety parameters defined in the protocol. All data monitored on site are verified for accuracy and thoroughness using the most appropriate source documents for all patients.

Signed informed consent documents and HIPAA documentation are monitored for all patients, along with those items outlined in the STOP-ALF Site Monitoring Plan.

Any omissions and corrections to data submitted to the WebDCU™ database are noted and queries are generated either on-site or remotely by the monitor and/or centrally by the SDCC staff.

The monitor may conduct a close-out monitoring visit either on-site or remotely, as determined by the SDCC staff based on the number of subject enrollments, amount and nature of outstanding items to be monitored, and if the monitor's direct access to the subjects' electronic medical record has been permitted by the institution. During a Site Closeout Visit, the monitor should follow the site close-out guidelines outlined in the current version of the STOP-ALF Site Monitoring Plan.

11 STATISTICAL PROCESS

11.1 Statistical Methods

Descriptive statistics will be used to evaluate safety, exploratory efficacy data, PK and PD.

11.2 Comparisons of Interest

Collected data will be evaluated overall and by cohort (patients with minimal renal dysfunction and those with compromised renal function).

11.3 Sample Size Determination

This is an exploratory pilot study and no formal sample size calculation was performed for this study.

11.4 Analysis Population

The intent-to-treat (ITT) population will include all patients who consented to the study, completed screening and were initiated intravenous infusion of study drug. The ITT population will serve as the basis for a sensitivity analysis of the PP results for all endpoints.

The per-protocol (PP) population (evaluable population) will include all patients who receive at least 72h of OCR-002 in accordance with protocol timelines. The PP population will be used for the primary analysis of all outcomes.

The safety population will include all patients who completed screening and were enrolled into the trial.

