Study Design	
This is a Phase 2a, multi-center, open-label study, conducted in two cohorts of patients diagnosed with acute liver failure/severe acute liver injury (ALF/ALI) who meet inclusion/exclusion criteria. Cohort 1 is defined as patients with ALF/ALI with minimal renal dysfunction at the time of enrollment (defined as a serum creatinine ≤ 1.5 mg/dL and mean arterial pressure of >65 mm Hg). Cohort 2 is defined as patients with ALF/ALI with compromised renal function (defined as a serum creatinine >1.5 mg/dL and <10 mg/dL with mean arterial pressure of >65 mm Hg).
 
Informed consent will be obtained from the patient and/or patient's legally authorized representative (LAR) or family member as defined in 21CFR50.3(m). All patients will receive medical care for acute liver failure/severe acute liver injury according to the institution's standards of care. Standard of care may include, but is not limited to, administration of N-acetylcysteine and consideration for orthotopic liver transplantation.
 
Up to 36 evaluable patients will be enrolled. An evaluable patient is one who has received an infusion of OCR-002 for at least 72 hours. It is expected that not every enrolled patient will be treated for at least 72 hours due to transplant, death or early hospital discharge. Due to this, we anticipate 25% of the enrolled population will fail to reach evaluable status. Therefore, we plan to enroll up to 50 patients in order

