4 OBJECTIVES AND ENDPOINTS

4.1 *Objectives*

4.1.1 **Primary Objective**

To evaluate the safety and tolerability of OCR-002 in patients with acute liver failure/severe acute liver injury.

Hypothesis: Treatment with OCR-002 is safe and tolerable in patients with acute liver failure/acute liver injury.

4.1.2 **Secondary Objectives**

To evaluate the steady state pharmacokinetic and pharmacodynamic profile of OCR-002 in patients with impaired and minimal renal dysfunction using urinary PAGN as a surrogate marker.

Hypothesis: A dose of 10-20g/24h (0.42-.83g/h) will achieve steady state plasma concentrations within 6-12h with little additional accumulation in the ALI/ALF setting.

To evaluate the effect of OCR-002 on ammonia levels in patients with acute liver failure/severe acute liver injury.

Hypothesis: Treatment with OCR-002 will reduce ammonia levels in patients with ALI/ALF.

To evaluate the effect of OCR-002 on neurological function in patients with acute liver failure/severe acute liver injury.

Hypothesis: Treatment with OCR-002 will improve neurological function in patients with acute liver failure/severe acute liver injury.

4.2 *Endpoints*

4.2.1 **Safety Endpoints**

Safety assessments will include: abbreviated physical examinations, vital signs (blood pressure, pulse rate, respiration rate, and body temperature), clinical laboratory tests (hematology and serum chemistry), 12-lead ECGs, and reported and observed adverse events.

4.2.2 **Exploratory Efficacy Endpoints**

- Ammonia concentrations.
- Neurological assessment will be measured by the Glasgow Coma Scale, the West Haven Criteria, and the Orientation log (O-log) (34).

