6.3.2 Enrollment

Patients will be considered enrolled into the study once informed consent has been obtained, all eligibility criteria are met, and the study drug infusion has been initiated. A study identification number will be assigned by the computer system that houses the study database. A Screen Failure Log will be maintained to capture basic information on all patients screened for the study but who failed to be enrolled. This would include demographic information and the reasons for failure to enroll.

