11.5 Interim Analysis

There are no interim analyses planned as this is an open-label study; however, safety data will be reviewed by the SRC continuously throughout the study period. In addition to specific dose level reports, quarterly safety reports on all enrolled patients will be provided to the SRC during the study period. These reports will include summary tables overall and by cohort and site on baseline characteristics, treatment completions and reasons for early treatment withdrawals, study completions rates and all outcomes related to safety information including all adverse events and serious adverse events.

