11.7 Safety Assessments

11.7.1 Adverse Events

Adverse events will be classified into standard terminology using the Medical Dictionary for Regulatory Activities (MedDRA). Adverse events will be listed by reported verbatim term and MedDRA-preferred term, start and stop date and time, study day, duration, severity, relationship to study drug, and seriousness. Additionally, data may be grouped for analysis by different levels of the MedDRA hierarchy. The incidence of AEs, the incidence of treatment-related AEs, and the severity of AEs will be tabulated by cohort.

The number and percentage of patients with SAEs and treatment-related SAEs and patients who withdraw due to an AE will be tabulated by cohort.

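### The primary safety result is restricted to patients infused for at least 72 h, so early deaths and early toxicity stops cannot appear in it

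*Combined protocol and SAP*

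**What the plan says.** The primary objective in Section 4.1.1 is: "To evaluate the safety and tolerability of OCR-002 in patients with acute liver failure/severe acute liver injury". Section 4.2.1 lists physical examinations, vital signs, laboratory tests, ECGs and adverse events as the safety endpoints.

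Section 11.4 defines three sets:

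- **PP (evaluable):** patients with at least 72 h of OCR-002. Its role is: "The PP population will be used for the primary analysis of all outcomes".
- **ITT:** consented, screened patients whose infusion was started. Its role is: "The ITT population will serve as the basis for a sensitivity analysis of the PP results for all endpoints".
- **Safety:** "The safety population will include all patients who completed screening and were enrolled into the trial". No analysis is attached to it.

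Under Section 6.3.2 a patient counts as enrolled only once consent is obtained, "all eligibility criteria are met, and the study drug infusion has been initiated". The safety and ITT sets therefore hold essentially the same patients.

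Section 11.7 and the Safety Analysis entry of the synopsis name no population. Section 11.7.1 says that "patients who withdraw due to an AE will be tabulated by cohort", along with SAEs. The memorandum at the end of the document confirms that Section 11 is the whole statistical plan.

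On expected losses, the synopsis (Study Design) says "we anticipate 25% of the enrolled population will fail to reach evaluable status" and attributes this to transplant, death or early discharge.

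**The concern.** Membership of the primary set depends partly on the outcome being measured. A patient who dies early cannot accrue 72 h of infusion. Section 6.3.4 lists toxicity of Grade 3 or higher, QT prolongation, torsades and shock among the reasons for stopping treatment, and any of these can occur before 72 h. Stopping is at the investigator's discretion, so an early event does not always remove a patient. However, Section 7.5 does not allow the drug to be restarted once an interruption exceeds 2 h, so any such interruption before 72 h does remove the patient.

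The effect reaches beyond the first 72 h. Section 6.3.5 keeps early stoppers under follow-up through the 30-day study period, but their later SAEs and deaths are outside the PP set too. The table of withdrawals due to an AE, run on PP, cannot show anyone who stopped treatment before 72 h.

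At stake is the headline answer to the primary question. It would describe safety among patients who tolerated and survived three days of drug. This bears particularly on Dose Level 4, where infusion starts at the full level without titration and early tolerability is a central question.

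**Working it through.** **1. Which set the rule assigns to safety.** Section 11.4 makes PP primary for every outcome, without exception, and makes ITT a sensitivity analysis for every endpoint. Section 4.2.1 classes adverse events, laboratory tests, vital signs and ECGs as endpoints. Section 11.5 uses the word outcomes in the same way, listing "all outcomes related to safety information including all adverse events and serious adverse events". Nothing elsewhere in Section 11 assigns safety to another set. Read literally, PP is primary for safety.

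**2. Reproducing the plan's enrolment figure.** Inputs from the synopsis: 36 evaluable patients, 25% loss, up to 50 enrolled.

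- 36 / (1 − 0.25) = 48, which agrees with the stated maximum of 50 to within 2 patients.

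**3. Share of treated patients outside the primary safety set.**

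- With 48 enrolled: 48 − 36 = 12, and 12/48 = 25%.
- With 50 enrolled: 50 − 36 = 14, and 14/50 = 28%.

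**4. What PP can show for deaths or treatment stops before 72 h.** The count is zero by definition. Section 11.6 attaches two-sided 95% intervals to point estimates. For zero events the exact (Clopper-Pearson) upper limit is 1 − 0.025^(1/n).

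- All PP patients: 0/36, upper limit 9.7%.
- Per cohort (about 18 each, Section 5.1): 0/18, upper limit 18.5%.

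These limits surround a structural zero and carry no information about the drug.

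**5. What the all-treated set would show.** Each such patient adds 1/50 = 2.0 to 1/48 = 2.1 percentage points to the all-treated rate and nothing to the PP rate. The documents do not split the expected losses by reason, so the counts below are assumptions.

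| Early deaths or toxicity stops (assumed) | All treated, n = 50 (exact 95% CI) | PP, n = 36 |
|---|---|---|
| 2 | 4% (0.5–13.7%) | 0/36 |
| 3 | 6% (1.3–16.5%) | 0/36 |
| 6 | 12% (4.5–24.3%) | 0/36 |

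**6. Effect on overall mortality.** Section 9.1.2 gives 28–30% mortality for acetaminophen ALF. Take 28% of 50, or 14 deaths, and let s be the assumed share of deaths in patients with under 72 h of infusion. PP mortality is 14(1 − s)/36.

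- s = 25%: 10.5/36 = 29.2%.
- s = 50%: 7/36 = 19.4%.
- s = 75%: 3.5/36 = 9.7%.

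The PP figure can fall to about a third of the all-treated 28%. When few deaths are early it can be slightly higher, because patients lost to discharge or transplant also leave the denominator.

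**The case against.** The strongest reply is that a safety population almost identical to ITT makes sense only if it was meant for the safety tables, and that a statistician could reasonably run Section 11.7 on it. That may well be the intention. But it has to override an explicit sentence, and with no separate SAP nothing else supplies the rule.

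Three further points stand and limit the finding:

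- **Early events are not lost.** They appear in the ITT sensitivity analysis, in the quarterly SRC reports on all enrolled patients (Section 11.5) and in the SRC's end-of-study review (Section 9.7). The fault lies in the result labelled primary.
- **The trial is descriptive.** It is not powered, and no success criterion rests on the PP safety table.
- **The numbers have limits.** 0/36 restates the PP definition, and Section 11.7.1 plans no table of events before 72 h. The PP version of its table would still show later AE withdrawals and, in patients who reached 72 h, all their AEs and SAEs. The 2-to-6 range is assumed, and the synopsis does not name toxicity among the expected reasons for loss.

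None of this changes what the stated rule does. SRC reports do not define the trial's primary result, and a sensitivity analysis does not replace it.

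**Conclusion.** The point holds. As written, Section 11.4 takes every death and every treatment stop before 72 h of infusion out of the primary result for the primary objective, and it leaves the safety population without a use. The excluded share is 25% to 28% of treated patients, which rests only on the plan's figures of 36 evaluable, 25% loss and up to 50 enrolled. The all-treated rates of 4% to 12% and the mortality figures rest on assumed splits and are illustrations.

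The direction is clear for early intolerance that ends treatment and for early death: both are understated. It is not established for overall AE rates, because patients discharged or transplanted early are excluded as well. This needs correcting because it concerns the primary objective.

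**What to change.** In Section 11.4, state that all safety and tolerability summaries (AEs, SAEs, deaths, discontinuations, laboratory tests, vital signs, ECGs) use the safety population as primary, meaning every patient whose infusion was started. Limit the sentence that makes PP primary to PK/PD and exploratory efficacy, and keep the ITT sensitivity analysis. Name the safety population in Section 11.7.

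The cost is one or two sentences and a population label. The set is already defined, and Section 8.3 already requires end-of-infusion and 24 h assessments for every infused patient, including early stoppers. For safety endpoints, the retained ITT analysis would largely duplicate the new primary analysis. The other consequence is that reported safety rates may look less favourable.

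The ammonia and neurological results would still be primary on PP and subject to the same selection. The ITT analysis should be reported beside them.

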In aggregate, these studies supported an initial study using a 10g/24 hours dose of OCR-002 as suitable for an early phase study in ALF patients. As STOP-ALF represents the first study of OCR-002 conducted in patients with ALF, the administration of the study drug in three ascending dose levels (Dose Levels 1 through 3) will be implemented as follows and in the protocol for up to 24 evaluable subjects:

The maximum target infusion rate will be 0.42g/h, which is equivalent to 10g administered over 24h.

The infusion rate will be staged for each patient. The initial infusion rate will be 0.14g/h (33% of target dose). The dose will be then increased to 0.28g/h (66% target), and 0.42g/h (100% target) in successive 12h intervals based on a patient safety evaluation by the Investigator.

Patient safety and tolerability at an increased loading dose are supported by the pharmacokinetic data and plasma ammonia levels obtained from the ongoing clinical study Phase 2 OP-GIB conducted in Spain, in which cirrhotic patients with active gastrointestinal hemorrhage receive double-blind treatment, i.e., placebo or OCR-002 at 10 g per 24 hours as a constant intravenous infusion for 5 days.

Ocera began over a year ago a large ongoing trial of OCR-002 in hospitalized patients with cirrhosis and associated hyperammonemia (OCR002-HE209, STOP-HE). In STOP-HE, a placebo-controlled, randomized, double-blind clinical trial designed to evaluate the safety, pharmacokinetics and efficacy of intravenously-administered OCR-002 in resolving neurocognitive symptoms of acute HE in hospitalized cirrhotic patients with elevated ammonia, either OCR-002 or placebo is administered to patients intravenously for up to five days along with standard of care, at doses of 20, 15, or 10 grams over 24 hours based on the patient's degree of liver impairment. In this study, there is no ascending or loading dose being implemented.

Therefore, up to 12 additional evaluable patients will be enrolled at Dose Level 4 as listed below:

Dose Level 4: For patients assigned to this dose level, the infusion will be initiated at the full dose level of 20g/24hr for a maximum time of 120 hours (approximately .83g/h), provided the dose level is well tolerated with no noteworthy side effects.

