 - West-Haven Scale; and
 - O-Log Scale;
- Continuous monitoring and collection of mean arterial pressure;
- Continuous monitoring and collection of intracranial pressure (ICP) (if applicable); and
- AE review and reporting.

End of Treatment Day 3 at 72 Hours / Day 4 at 0 h

- Continue on maintenance infusion of OCR-002;
- Collection of concomitant medications (if applicable);
- Collection of blood for hematology, coagulation, clinical chemistry, ammonia and PK;
- Urinalysis*;
*Urinalysis: dipstick plus microscopic evaluation of sediment, if clinically indicated.
- Vital signs and abbreviated physical exam;
- Neurological battery, including:
 - Glasgow Coma Scale;
 - West-Haven Scale; and
 - O-Log Scale;
- 12-lead ECG;

- Document urine volume, take a sample from 48-72h urine volume, and start 72-96h urine collection;
- Continuous monitoring and collection of mean arterial pressure;
- Continuous monitoring and collection of intracranial pressure (ICP) (if applicable); and
- AE review and reporting.

End of Treatment Day 4 at 96 Hours / Day 5 at 0 h

- Continue on maintenance infusion of OCR-002;
- Collection of concomitant medications (if applicable);
- Collection of blood for hematology, coagulation, clinical chemistry, ammonia and PK;
- Urinalysis*;
 - * Urinalysis: dipstick plus microscopic evaluation of sediment, if clinically indicated.
- Vital signs and abbreviated physical exam;
- Neurological battery, including:
 - Glasgow Coma Scale;
 - West-Haven Scale; and
 - O-Log Scale;
- 12-lead ECG;
- Document urine volume, take a sample from 72-96h urine volume, and start ~~next 24-96~~-120h urine collection;
- Continuous monitoring and collection of mean arterial pressure;
- Continuous monitoring and collection of intracranial pressure (ICP) (if applicable); and
- AE review and reporting.

Completion of the Last Infusion (at time infusion is stopped)

The following assessments should be administered on all patients who received an infusion of the study drug, including those patients who received the full course of study drug treatment and those patients who do not complete the entire course of study drug treatment.

- Collection of concomitant medications (if applicable);
- Collection of blood for hematology, coagulation, clinical chemistry, ammonia and PK;
- Urinalysis*;
 - * Urinalysis: dipstick plus microscopic evaluation of sediment, if clinically indicated.
- Vital signs and abbreviated physical exam;
- Neurological battery, including:

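### The primary PK summaries are limited to patients infused for at least 72 h, although steady state is hypothesised, and can be observed, well before then and early stoppers are sampled too

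*Combined protocol and SAP*

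**What the plan says.** Section 11.4 defines three populations. The per-protocol (evaluable) set "will include all patients who receive at least 72h of OCR-002 in accordance with protocol timelines", and it is primary for everything: "The PP population will be used for the primary analysis of all outcomes". The ITT set, meaning every patient whose infusion was started, has a supporting role: "The ITT population will serve as the basis for a sensitivity analysis of the PP results for all endpoints". No PK population is defined. Section 11.7.6 lists Cmax, Css, CLss and interval AUC, promises individual listings and summary statistics, and does not say which population the summaries use. The memorandum at the end of the file confirms that there is no SAP apart from Section 11.

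The PK hypothesis in Section 4.1.2 reads: "A dose of 10-20g/24h (0.42-.83g/h) will achieve steady state plasma concentrations within 6-12h with little additional accumulation in the ALI/ALF setting".

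Section 8.3 schedules PK blood at 12, 24, 36, 48, 72 and 96 h. It repeats the draw at the end of the last infusion and 24 h afterwards in all infused patients, "including those patients who received the full course of study drug treatment and those patients who do not complete the entire course".

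The Synopsis (Study Design) expects that "not every enrolled patient will be treated for at least 72 hours due to transplant, death or early hospital discharge". It puts the loss at 25% and plans up to 50 enrolled patients to obtain 36 evaluable ones. Section 6.3.4 adds further grounds for stopping, among them Grade 3 or higher toxicity, QT prolongation and shock.

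**The concern.** The 72 h entry rule does not match the PK question. Steady state is expected within hours of reaching the target rate, yet a patient infused for 48 h, with four scheduled on-treatment samples plus the stop and post-stop samples, does not enter the primary PK summary.

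The rule also conditions on an event after baseline. Reaching 72 h means being alive, not transplanted, not discharged and still tolerating the drug. Any of these may be related to how the patient handles the drug. The primary estimate then describes exposure in patients still on drug at 72 h, whereas the stated objective concerns exposure in ALF/ALI patients given the drug.

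At stake are the headline Css, CLss, Cmax and early AUC values that would inform dosing at 10-20 g/24h, their between-patient spread, and their precision.

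**Working it through.** **1. The plan's own figure.** Inputs (Synopsis): 36 evaluable patients, 25% non-evaluable. 36 / (1 - 0.25) = 48, in line with the stated ceiling of 50. Treated patients outside the primary PK set: 48 - 36 = 12 (12/48 = 25%) up to 50 - 36 = 14 (14/50 = 28%).

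**2. When the hypothesised steady state falls.** Inputs: rates and switch times in Section 5.2. Window = start of target rate + 6 to 12 h.
- Dose Level 4 (20 g/24h from hour 0): hours 6-12.
- Dose Level 3 (10 g/24h from hour 24): 24 + 6 = 30 to 24 + 12 = 36.
- Dose Levels 1 and 2 (3.33 and 6.65 g/24h) lie below the range named in the hypothesis.

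Both windows end at least 72 - 36 = 36 h before the entry threshold.

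**3. Samples available before 72 h.** Scheduled on-treatment PK draws: 12, 24, 36 and 48 h, so four, plus the stop and 24 h post-stop draws. There is no PK draw at 6 h (only ammonia), and the collection window is +/-3 h. The 6 h end of the hypothesis therefore cannot be checked in any population.

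**4. Precision.** Half-width of a 95% CI for a mean is proportional to t(0.975, n-1)/sqrt(n), at equal SD.
- 36 versus 48: 1.17.
- 36 versus 50: 1.19.
- Dose Level 4 alone, 12 evaluable from 12/0.75 = 16: 1.19.

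These are upper bounds. Patients stopping before 12 h miss the scheduled 12 h sample, not every early stopper will have every parameter, and the 36 versus 48-50 comparison pools all dose levels.

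**5. Possible bias.** The documents give no PK variability and no relation between exposure and stopping, so everything in this step is assumption. Let f be the excluded share and r the ratio of mean exposure in early stoppers to that in completers. The all-treated mean, in units of the completer mean, is (1 - f) + f x r, and the relative error of the primary mean is 1/[(1 - f) + f x r] - 1.

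| r | f = 0.25 | f = 0.28 |
|---|---|---|
| 0.75 | +6.7% | +7.5% |
| 1.0 | 0 | 0 |
| 1.25 | -5.9% | -6.5% |
| 1.5 | -11.1% | -12.3% |
| 2.0 | -20.0% | -21.9% |

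A second approach assumes lognormal exposure with CV 50% (log SD s = sqrt(ln 1.25) = 0.472) and a correlation rho of 0.5-0.8 between log exposure and disease severity.
- If exactly the most severe 25% are excluded, the retained mean relative to the full mean is Phi(0.674 - rho x s)/0.75. For rho = 0.5 this is 0.669/0.75 = 0.89, or 11% low. For rho = 0.8 it is 0.617/0.75 = 0.82, or 18% low.
- If severity only raises the odds of exclusion by 1.5 to 3 fold per SD, with the same 25% excluded, the mean is 2-9% low.
- If the excluded patients are mainly early discharges, the sign reverses. At zero correlation there is no bias.

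**The case against.** The strongest reply is that the plan already contains the remedy. ITT is a sensitivity analysis for all endpoints, individual PK parameters are listed, and the study is descriptive, with no sample size calculation and no PK success criterion. On this view the proposal mostly exchanges the primary and sensitivity labels. Part of this stands: nothing is destroyed, and a reader who infers that early stoppers' PK data are discarded goes beyond the text. But Section 4.2 names only safety and exploratory efficacy endpoints, so whether the ITT analysis reaches PK is open. Even if it does, the selected set stays the headline, reported with the 95% CIs that Section 11.6 promises.

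Second, longer infusions do matter for part of the question. Showing little further accumulation, and AUC over several dosing days, needs later samples; a Dose Level 3 patient stopped before hour 24 never receives 10 g/24h; and one 12 h sample cannot by itself show steady state. All of this stands. It supports a data requirement for each parameter, not a 72 h entry rule for every PK summary.

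Third, a reader might infer that the rule removes the patients with the highest exposure and so favours the little-accumulation hypothesis. The documents do not support that. The reasons given for the 25% loss cover both very sick patients and patients well enough to leave. Section 3.3.2 describes another trial that gives the drug "at doses of 20, 15, or 10 grams over 24 hours based on the patient's degree of liver impairment", but nowhere states that exposure rises with severity in ALF or that patients with high exposure stop sooner. The Cmax-related adverse effects it reports arose above 10 g over 4 h (10/4 = 2.5 g/h), against at most about 0.83 g/h here, and the same section says that infusion over 24 h avoids them.

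**Conclusion.** The point holds for the primary PK analysis. Section 11.4 ties every primary PK summary to 72 h of infusion, which the steady-state question does not need, and so sets up to 12-14 of 48-50 treated patients (25-28%) outside the headline on the basis of events after baseline. The count rests on the plan's own 25% loss and its enrolment ceiling.

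The cost in precision is at most about 17-19% in CI width. Any bias ranges from none, if stopping is unrelated to exposure, to roughly 10-20% of the mean under strong assumptions about that relation; its direction cannot be derived from the documents. No power or error rate is affected. This is an inexpensive improvement worth making, not a flaw that invalidates the PK results.

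**What to change.** In Section 11.4, exempt PK from the all-outcomes rule and define a primary PK population: every patient who started OCR-002 and has at least one measurable post-dose plasma sample. Each parameter then uses every patient who has the samples it needs:
- Cmax: all patients in the PK population.
- Css and CLss: patients with at least 12 h at a constant rate.
- AUC: each completed dosing day.
- Accumulation: only patients with later samples.

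Show n for each parameter and day. Keep the 72 h set as the PK sensitivity analysis, and name the PK population in Section 11.7.6.

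The cost is about one paragraph of text. No new samples, visits or patients are needed, because Section 8.3 already requires the draws. The downside is that n varies by parameter and day, so summaries for different days will not describe identical patients.
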